9.3 Analysis of Laboratory Data

Data collected from central and local laboratories, including additional laboratory testing due to an SAE, will be used in all analyses, except for Baseline where SAE-related laboratory assessments on or before the first dose of study drug will be excluded. The clinical laboratory tests defined in the protocol operations manual (e.g., hematology and clinical chemistry) will be summarized.

Each laboratory variable will be summarized for all time points (starting with Baseline) with the number of non-missing observations, mean and standard deviation, median, minimum and maximum. Mean change from baseline to each applicable post-baseline visit will be summarized for selected laboratory variables, with the number of observations, baseline mean, and visit mean.

The baseline and post-baseline laboratory observations will be categorized as Grade 0, Grade 1, Grade 2, Grade 3, and Grade 4 and shifts from baseline grade to worst on-therapy grade will be summarized. A similar shift table will be provided to summarize shifts from baseline to the final post-baseline value. Toxicity grading scale is based on CTCAE version 4.03 ([Appendix B](#)).

Laboratory abnormalities will be evaluated based on Potentially Clinically Significant (PCS) criteria ([Appendix B](#)). For each laboratory PCS criterion, the number and percentage of subjects who have a laboratory value meeting the criteria will be summarized. Listings will be provided to summarize subject-level laboratory data for subjects meeting PCS criteria.

In addition, ALT/SGPT, AST/SGOT, alkaline phosphatase, and total bilirubin will be categorized as follows:

- ALT $\geq 3 \times$ ULN
- ALT $\geq 5 \times$ ULN
- ALT $\geq 10 \times$ ULN
- ALT $\geq 20 \times$ ULN

- $\text{AST} \geq 3 \times \text{ULN}$
- $\text{AST} \geq 5 \times \text{ULN}$
- $\text{AST} \geq 10 \times \text{ULN}$
- $\text{AST} \geq 20 \times \text{ULN}$
- $\text{TBL} \geq 2 \times \text{ULN}$
- $\text{Alkaline phosphatase} \geq 1.5 \times \text{ULN}$
- $(\text{ALT and/or AST} \geq 3 \times \text{ULN}) \text{ and } (\text{TBL} \geq 1.5 \times \text{ULN})$
- $(\text{ALT and/or AST} \geq 3 \times \text{ULN}) \text{ and } (\text{TBL} \geq 2 \times \text{ULN})$

where ULN is the upper limit of normal.

A listing of potentially clinically significant liver function laboratory values will be provided. The listing will include all subjects who met any of the following 4 criteria:

- $\text{ALT} \geq 3 \times \text{ULN}$, or
- $\text{AST} \geq 3 \times \text{ULN}$, or
- $\text{Alkaline phosphatase} \geq 1.5 \times \text{ULN}$, or
- $\text{Total bilirubin} \geq 1.5 \times \text{ULN}$.

A listing of possible Hy's Law cases, defined as those who meet all of the following conditions at any post-baseline visit will be provided:

- ALT of $> 3 \times \text{ULN}$ or AST of $> 3 \times \text{ULN}$,
- Total bilirubin $\geq 2 \times \text{ULN}$.

9.4 Analysis of Vital Signs

Vital sign measurements of systolic and diastolic blood pressure, pulse rate, and body temperature will be summarized.

Each vital sign variable will be summarized for all time points (starting with Baseline) with the number of non-missing observations, mean and standard deviation, median,

minimum and maximum. Mean change from baseline to each applicable post-baseline visit will be summarized for each vital sign variable, with the number of observations, baseline mean, and visit mean.

Vital sign variables will be evaluated based on potentially clinically significant (PCS) criteria ([Appendix B](#)). For each vital sign PCS criterion, the number and percentage of subjects who have a vital sign value meeting the criteria will be summarized. Listings will be provided to summarize subject-level vital sign data for subjects meeting PCS criteria.

10.0 Other Analyses

Not applicable.

11.0 Interim Analyses

After 30 ongoing subjects complete Week 8 assessments, an interim analysis will be performed in order to explore if proof of concept has already been demonstrated. This interim analysis will inform the planning of future Phase 2b and 3 studies. Enrollment into the induction period will continue until approximately 40 subjects have been enrolled. For this proof of concept study, no alpha adjustment will be conducted for this interim analysis.

11.1 Data Monitoring Committee

An internal data monitoring committee (DMC) will review unblinded safety data from the study. The primary responsibility of the DMC will be to protect the safety of the subjects participating in this study.

A DMC charter describes the roles and responsibilities of the DMC members, frequency of data reviews, relevant data to be assessed, and general operations.

12.0 Overall Type-I Error Control

No multiplicity adjustment will be performed for this single-arm open-label proof of concept study.

13.0 Version History

Table 1. SAP Version History Summary

Version	Date	Summary
1.0	11 June 2018	Original version
2.0	15 Aug 2018	
Section 6.0 Secondary Endpoints: Highlighted key secondary endpoints and moved the rest to exploratory endpoints.
 
Rationale: to align with protocol amendment per regulatory feedback.
 
Section 7.0 Statistical Analyses for Efficacy: Updated sample size estimation language.
 
Rationale: To align with protocol amendment per regulatory feedback.
 
Section 11.0 Efficacy Analyses: Added priors for sensitivity analysis.
 
Rationale: To align with regulatory feedback.

3.0	10 Feb 2021	
Section 7.0 Demographics, baseline characteristics added
 
Section 8.0 Analysis method updated per Protocol updates
 
Appendix C: PCS criteria updated
 
Section 8.3.3, Section 8.3.4 and Appendix D: updated historical rate █ as primary analysis due to new UPA UC phase 3 data available after protocol finalization and included historical rate █ which was specified in protocol as sensitivity analysis.

Appendix A. Protocol Deviations

The number and percentage of subjects who reported at least one of the following protocol deviation categories will be provided.

- Subject entered into the study even though s/he did not satisfy entry criteria.
- Subject developed withdrawal criteria during the study and was not withdrawn.
- Subject received wrong treatment or incorrect dose of study.
- Subject took prohibited concomitant medication.

Appendix B. Common Toxicity Criteria (CTC) Grade for Laboratory Data

Test	Grade 1	Grade 2	Grade 3	Grade 4
Chemistry Variables				
SGPT/ALT increased	> ULN – 3.0 × ULN	> 3.0 – 5.0 × ULN	> 5.0 – 20.0 × ULN	> 20.0 × ULN
SGOT/AST increased	> ULN – 3.0 × ULN	> 3.0 – 5.0 × ULN	> 5.0 – 20.0 × ULN	> 20.0 × ULN
GGT increased	> ULN – 2.5 × ULN	> 2.5 – 5.0 × ULN	> 5.0 – 20.0 × ULN	> 20.0 × ULN
ALP increased	> ULN – 2.5 × ULN	> 2.5 – 5.0 × ULN	> 5.0 – 20.0 × ULN	> 20.0 × ULN
TBL increased	> ULN – 1.5 × ULN	> 1.5 – 3.0 × ULN	> 3.0 – 10.0 × ULN	> 10.0 × ULN
Creatinine increased	> ULN – 1.5 × ULN	> 1.5 – 3.0 × ULN	> 3.0 – 6.0 × ULN	> 6.0 × ULN
CPK increased	> ULN – 2.5 × ULN	> 2.5 – 5.0 × ULN	> 5.0 – 10.0 × ULN	> 10.0 × ULN
Total Cholesterol increased	> ULN - 7.75	> 7.75 - 10.34	> 10.34 - 12.92	> 12.92
Albumin decreased	< LLN – 30 g/L	< 30 – 20 g/L	< 20 g/L	-
Triglycerides increased	1.71 - 3.42 mmol/L	> 3.42 - 5.7 mmol/L	> 5.7 - 11.4 mmol/L	> 11.4 mmol/L
Glucose	< LLN - 3.0 mmol/L or > ULN - 8.9 mmol/L	< 3.0 - 2.2 mmol/L or > 8.9 - 13.9 mmol/L	< 2.2 - 1.7 mmol/L or > 13.9 - 27.8 mmol/L	< 1.7 mmol/L or > 27.8 mmol/L
Sodium	< LLN – 130 mmol/L or > ULN – 150 mmol/L	> 150 – 155 mmol/L	< 130 – 120 mmol/L or > 155 – 160 mmol/L	< 120 mmol/L or > 160 mmol/L
Potassium	< LLN - 3.0 mmol/L or > ULN - 5.5 mmol/L	< LLN - 3.0 mmol/L or > 5.5 - 6.0 mmol/L	< 3.0 - 2.5 mmol/L or > 6.0 - 7.0 mmol/L	< 2.5 mmol/L or > 7.0 mmol/L
Calcium	< LLN - 2.0 mmol/L or > ULN - 2.9 mmol/L	< 2.0 - 1.75 mmol/L or > 2.9 - 3.1 mmol/L	< 1.75 - 1.5 mmol/L or > 3.1 - 3.4 mmol/L	< 1.5 mmol/L or > 3.4 mmol/L

Test	Grade 1	Grade 2	Grade 3	Grade 4
Hematology Variables				
Hemoglobin decreased	< LLN – 100.0 g/L	< 100.0 – 80.0 g/L	< 80.0 g/L	-
Neutrophil count decreased	< LLN – 1.5×10^9 /L	< 1.5 – 1.0×10^9 /L	< 1.0 – 0.5×10^9 /L	< 0.5×10^9 /L
WBC decreased	< LLN – 3.0×10^9 /L	< 3.0 – 2.0×10^9 /L	< 2.0 – 1.0×10^9 /L	< 1.0×10^9 /L
Lymphocyte count decreased	< LLN – 0.8×10^9 /L	< 0.8 – 0.5×10^9 /L	< 0.5 – 0.2×10^9 /L	< 0.2×10^9 /L
Lymphocyte count increased	-	> 4.0 – 20.0×10^9 /L	20.0×10^9 /L	-
Platelets count decreased	< LLN - 75.0×10^9 /L	< 75.0 - 50.0×10^9 /L	< 50.0 - 25.0×10^9 /L	< 25.0×10^9 /L

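### SAP Appendix B gives low potassium the same range for Grades 1 and 2, and the grade shift tables for four two-sided analytes do not separate low from high values

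*SAP*

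**What the plan says.** SAP Section 9.3 places baseline and post-baseline laboratory observations in Grades 0 to 4, and "shifts from baseline grade to worst on-therapy grade will be summarized". A second shift table runs from baseline to the final post-baseline value. The scale is said to be based on CTCAE 4.03 and is set out in Appendix B.

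The potassium row of Appendix B reads:

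- Grade 1: "< LLN - 3.0 mmol/L or > ULN - 5.5 mmol/L"
- Grade 2: "< LLN - 3.0 mmol/L or > 5.5 - 6.0 mmol/L"
- Grade 3: "< 3.0 - 2.5 mmol/L or > 6.0 - 7.0 mmol/L"
- Grade 4: "< 2.5 mmol/L or > 7.0 mmol/L"

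Three other analytes also have a single row with a low and a high range joined. Their Grade 1 cells are "< LLN - 3.0 mmol/L or > ULN - 8.9 mmol/L" for glucose, "< LLN – 130 mmol/L or > ULN – 150 mmol/L" for sodium and "< LLN - 2.0 mmol/L or > ULN - 2.9 mmol/L" for calcium. Lymphocytes, by contrast, have one row for decreases and another for increases.

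Section 9.3 gives no rule for a value that meets two grades. It does not say whether shifts are tabulated separately for low and high values.

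**The concern.** A grade used in a shift table has to be a function of the value: one value, one grade. The potassium row breaks this on the low side between 3.0 mmol/L and LLN. Appendix B carries no non-numeric criterion that could separate Grade 1 from Grade 2, so two programmers following the SAP could fill the same cells differently and both be compliant.

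The second issue is direction. If low and high values share one 0-to-4 scale, the worst grade does not tell the reader which way the value moved. A subject who crosses from one side of the normal range to the other can appear unchanged or improved.

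Safety and tolerability are part of the study objective. The current design enrols no concurrent control group, so readers will look at the absolute counts in these tables. Those counts should not depend on coding order.

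**Working it through.** No sample size, power or error rate is involved, and the plan states no figure to reproduce. The check compares cells and grades example values.

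**Step 1. Low-side ranges of the four joint rows (SAP Appendix B, mmol/L).**

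| Analyte | Grade 1 | Grade 2 | Grade 3 | Grade 4 |
|---|---|---|---|---|
| Glucose | below LLN to 3.0 | below 3.0 to 2.2 | below 2.2 to 1.7 | below 1.7 |
| Sodium | below LLN to 130 | none | below 130 to 120 | below 120 |
| Potassium | below LLN to 3.0 | below LLN to 3.0 | below 3.0 to 2.5 | below 2.5 |
| Calcium | below LLN to 2.0 | below 2.0 to 1.75 | below 1.75 to 1.5 | below 1.5 |

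Potassium is the only one of the four with identical Grade 1 and Grade 2 low ranges. Sodium also moves straight from Grade 1 to Grade 3 on the low side, but it does so by leaving low Grade 2 blank, so each sodium value has one grade.

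**Step 2. Which potassium values get two grades.** The documents give no normal range for potassium, so LLN was assumed at 3.3, 3.5 and 3.6 mmol/L, with ULN at 5.0, 5.1 and 5.3. Values from 2.0 to 7.5 were graded in steps of 0.1.

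| Assumed LLN | Values meeting both Grade 1 and Grade 2 | High values meeting two grades |
|---|---|---|
| 3.3 | 3.0 to 3.2 | none |
| 3.5 | 3.0 to 3.4 | none |
| 3.6 | 3.0 to 3.5 | none |

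Whatever the LLN, the ambiguous band runs from 3.0 to just below it. Below 3.0, each value has one grade (3 or 4). If a program takes the higher matching grade, low Grade 1 is always empty. If it takes the lower, low Grade 2 is always empty.

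**Step 3. Direction, with the rows programmed as printed.**

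| Baseline | On therapy | Grades shown | Apparent shift |
|---|---|---|---|
| 6.5 | 2.8 | 3 to 3 | none |
| 5.8 | 3.2 | 2 to 1, or 2 to 2 | improvement, or none |
| 5.4 | 3.2 | 1 to 1, or 1 to 2 | none, or worsening |

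These results are the same under all three assumed normal ranges. In each example the subject moved from a high to a low value. In the last two, the apparent shift also depends on how the Step 2 tie is broken.

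**Step 4. Tables reached.** Both planned shift tables (worst on-therapy grade and final value) use this scale.

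**The case against.** Four points can be made on the other side.

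*The scale may simply be reproduced.* A reader might infer that low potassium is being misgraded. The documents do not support that. They cite CTCAE 4.03 but do not reproduce it, so they do not show whether the repeated range is a slip or follows the source, or which grade is intended. This stands: what is shown is a rule that does not yield a unique grade, not a wrong grade.

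*Direction is kept elsewhere.* A reader might infer that the safety report cannot tell low from high. That also goes too far. Appendix C Table 3 has separate columns for very low and very high values of all four analytes at Grade 3 or greater. Section 9.3 plans counts, percentages and listings for each of those criteria, and minimum and maximum values at each time point. Protocol Section 7.4 speaks of shift tables and listings based on the laboratory's normal range. Section 9.3 fixes no table layout and does not exclude a split by direction. This largely stands. What remains is that the Appendix C criteria start at Grade 3, so they do not reach the ambiguous potassium band or any Grade 1 or 2 change. Minima and maxima do not count subjects.

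*Nothing turns on it.* Potassium is absent from the protocol's toxicity management table and is not an adverse event of special interest. No decision rule uses an Appendix B grade. This stands and limits the severity.

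*Frequency is unknown.* The protocol names bloody diarrhea as a hallmark symptom of the disease, but nowhere says low potassium is expected or how often. No count of affected subjects can be drawn from the documents.

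**Conclusion.** The point holds as a minor defect. Appendix B cannot give a unique grade to potassium from 3.0 mmol/L to just below LLN. The split between low Grades 1 and 2 in both shift tables would therefore be set by programming order. For glucose, sodium, potassium and calcium, the shift tables mix directions if the rows are programmed as printed.

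The size is limited. One band of one analyte is ambiguous, and four analytes lack a stated direction in two descriptive tables. Low potassium Grades 3 and 4, the Appendix C counts and listings, and all efficacy analyses are untouched.

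The ambiguity itself rests only on the printed cells. The band's upper end depends on the laboratory's LLN, for which 3.3 to 3.6 mmol/L was assumed. The loss of direction rests on the rows being programmed as written.

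**What to change.** 1. In Appendix B, make the low-potassium grades mutually exclusive for grading on laboratory values alone. Leaving low Grade 2 blank, as the sodium row does, is the internally consistent choice, but it should be confirmed against the cited CTCAE version before it is adopted.
2. Split glucose, sodium, potassium and calcium into decreased and increased rows, as for lymphocytes, and state in Section 9.3 that shifts to worst grade and to final value are tabulated separately by direction.

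The cost is an edit to the appendix, a sentence in Section 9.3, and one additional directional summary per analyte in each shift table: 4 × 2 = 8. No new data are needed.

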Appendix C. Potentially Clinically Significant Criteria for Safety Endpoints

The criteria for Potentially Clinically Significant (PCS) laboratory findings are described in [Table 2](#) and [Table 3](#), and the PCS criteria for vital sign findings are described in [Table 4](#).

Table 2. Criteria for Potentially Clinically Significant Hematology Values

Hematology Variables	Units	Definition of Potentially Clinically Significant NCI CTCAE Grade 3 or Greater	
		Very Low	Very High
Hemoglobin	g/dL	< 8.0	
Neutrophil	10 ⁹ /L	< 1.0	
Lymphocytes	10 ⁹ /L	< 0.5	> 20.0
WBC count	10 ⁹ /L	< 2.0	
Platelets count	10 ⁹ /L	< 50.0	

Note: A post-baseline value must be more extreme than the baseline value to be considered a potentially clinically significant finding.

Table 3. Criteria for Potentially Clinically Significant Chemistry Values

Chemistry Variables	Units	Definition of Potentially Clinically Significant NCI CTCAE Grade 3 or Greater	
		Very Low	Very High
TBL	mcmol/L		$> 3.0 \times \text{ULN}$
ALP	U/L		$> 5.0 \times \text{ULN}$
SGOT/AST	U/L		$> 5.0 \times \text{ULN}$
SGPT/ALT	U/L		$> 5.0 \times \text{ULN}$
Albumin	g/L	< 20	
Glucose	mmol/L	< 2.2	> 13.9
Triglycerides	mmol/L		> 5.7
Creatinine	mcmol/L		$> 3.0 \times \text{ULN}$
Sodium	mmol/L	< 130	> 155
Potassium	mmol/L	< 3.0	> 6.0
Calcium	mmol/L	< 1.75	> 3.1
Total Cholesterol	mmol/L		> 10.34
GGT			$> 5.0 \times \text{ULN}$

Note: A post-baseline value must be more extreme than the baseline value to be considered a potentially clinically significant finding.

Table 4. Criteria for Potentially Clinically Significant Vital Sign Values

Vital Sign	Category	Criteria for Potential Clinically Significant Vital Signs
Systolic blood pressure (mmHg)	Low	Value ≤ 90 mmHg and decrease ≥ 20 mmHg from Baseline
	High	Value ≥ 160 mmHg and increase ≥ 20 mmHg from Baseline
Diastolic blood pressure (mmHg)	Low	Value ≤ 50 mmHg and decrease ≥ 10 mmHg from Baseline
	High	Value ≥ 100 mmHg and increase ≥ 10 mmHg from Baseline

Appendix D. Details for Historical Data Borrowing

D1. Historical Placebo Rate

The historical placebo rate [REDACTED] (Figure 2) is based on a robust meta-analysis of four historical trials evaluating centrally-assessed endoscopic improvement rate at Week 8 in a total of 325 placebo subjects with moderate to severe UC who failed prior anti-TNF or biologic therapy. These studies have similar population, inclusion and exclusion criteria as shown in [Table 5](#).

Table 5. Major Inclusion/Exclusion Criteria

[figure not shown]
Criteria	Historical Studies				Current Study
	OCTAVE-1	OCTAVE-2	Stelara Ph3	Upadacitinib M14-234	M15-722
Target Population	Sub population: Anti-TNF Failure	Sub population: Anti-TNF Failure	Sub population: Anti-TNF Failure	Subpopulation: Inadequate Response to Biologic Therapy	Prior Therapy (bio or tofa) Failure
Disease Activity	Baseline Mayo Score 6-12, Endoscopy subscore ≥ 2	Baseline Mayo Score 6-12, Endoscopy subscore ≥ 2	Baseline Mayo Score 6-12, Endoscopy subscore ≥ 2	Baseline Adapted Mayo Score 5-9, Endoscopy subscore ≥ 2	Baseline Adapted Mayo Score 5-9, Endoscopy subscore ≥ 2
Age	≥ 18 years	≥ 18 years	≥ 18 years	18-75 years	18-75 years
Prior Medication	Treatment experienced	Treatment experienced	Previously not treated with interleukin-12 or interleukin-23 antagonists	Previously not treated with JAK inhibitor (e.g., tofacitinib, baricitinib, filgotinib)	Previously treated with biologic therapy or tofa
Prohibited Medication	TNF antagonists	TNF antagonists	TNF antagonists	All biologic therapy or other JAK inhibitor	All biologic therapy or small molecule medication with potential impact on UC
Concomitant medication	Oral Aminosalicylates, oral glucocorticoids	Oral Aminosalicylates, oral glucocorticoids	Oral Corticosteroids, Aminosalicylates, immunomodulators	Oral Corticosteroids, Antibiotics, Aminosalicylates, and/or MTX	Oral Corticosteroids, Antibiotics, Aminosalicylates, or immunomodulators

In all the four trials, evidence of friability during endoscopy in subjects with a Mayo endoscopic subscore of 0 or 1 are conferred an endoscopic subscore of 2.

- Tofacitinib Phase 3
 - OCTAVE – Induction 1 (4/65)
 - OCTAVE – Induction 2 (4/65)
- Stelara Phase 3 UNIFI – Induction (11/161).

- [REDACTED]

Figure 2. Meta-analysis of Historical Placebo Rate

[figure not shown]

Prior to the database lock for the interim analysis, Upadacitinib UC Phase 3 study data became available. This Phase 3 study has the same population, inclusion and exclusion criteria with Upadacitinib UC Phase 2b study as shown in [Table 5](#).

- Tofacitinib Phase 3
 - OCTAVE – Induction 1 (4/65)
 - OCTAVE – Induction 2 (4/65)
- Stelara Phase 3 UNIFI – Induction (11/161).
- [REDACTED]
- [REDACTED]

A historical rate of [REDACTED] is obtained based on the meta-analysis, see [Figure 3](#) as below. The prior distribution was updated to [REDACTED]. Primary analysis will be conducted using this prior distribution for placebo.

Figure 3. Meta-analysis of Updated Historical Placebo Rate (including Upadacitinib UC Phase 3)

A large black rectangular redaction box covers the area where Figure 3 would have been located.

Historical rates for secondary endpoints at Week 8 are summarized in [Table 6](#) below.

Table 6. Historical Placebo Data for Secondary Endpoints

Endpoints	Historical Data					[REDACTED]	[REDACTED]
	OCTAVE-1/2	Stelara Ph3	[REDACTED]	[REDACTED]	[REDACTED]		
Clinical remission per Adapted Mayo score	NA	NA	[REDACTED]	[REDACTED]	[REDACTED]	[REDACTED]	[REDACTED]
Clinical response per Adapted Mayo score	NA	NA	[REDACTED]	[REDACTED]	[REDACTED]	[REDACTED]	[REDACTED]
Clinical response per Partial Adapted Mayo score	NA	NA	[REDACTED]	[REDACTED]	[REDACTED]	[REDACTED]	[REDACTED]
Clinical remission per Full Mayo score	NA	2/161	[REDACTED]	[REDACTED]	[REDACTED]	[REDACTED]	[REDACTED]
Endoscopic remission	NA	NA	[REDACTED]	[REDACTED]	[REDACTED]	[REDACTED]	[REDACTED]

[figure not shown]
NA = data are not applicable in subpopulation for respective endpoints.

Note that these five trials above enrolled a mixed population of subjects with anti-TNF-naïve or anti-TNF-IR, Bio-IR or non Bio-IR. Only Bio-IR subgroup data was used from these studies with mixture population.

D2. Prior Distribution Determination

Table 7 shows the false positive rate and true positive rate for different assumed true placebo response rates and ravagalimab response rates given the historical placebo response rate is [REDACTED] respectively. Note the range of this placebo rate is determined by the 90% confidence interval of placebo rate based on meta-analysis. False positive rate is calculated as the probability that the posterior probability of rate difference > 0 is larger than 90% assuming there is no treatment difference between ravagalimab and placebo. True positive rate is calculated as the probability that the posterior probability of rate

difference > 0 is larger than 90% assuming there is a 25% treatment difference between ravagalimab and placebo.

[REDACTED] prior corresponds to borrowing [REDACTED] subjects with a historical placebo rate of [REDACTED] and [REDACTED] prior corresponds to borrowing [REDACTED] subjects with a historical placebo rate of [REDACTED]. Operating characteristics of using [REDACTED] prior are the similar as using [REDACTED] prior based on the calculation.

Based on [Table 7](#), within 90% confidence interval of placebo rate [REDACTED] 20 historical subjects or less could be borrowed while controlling false positive rates $< 10\%$ and not exceeding in study sample size.

D3. Comparison between ravagalimab and Placebo.

Posterior probability of rate difference [REDACTED] given the endoscopic improvement at Week 8 results, i.e., [REDACTED] will be calculated as follows. [REDACTED] are the response rates of ravagalimab and placebo, respectively.

Let n and N be the number of responders and number of subjects at Week 8. The conjugate priors used for [REDACTED] are [REDACTED] respectively. Therefore the posterior distributions for $\theta_{\text{ravagalimab}}$ and θ_{Placebo} will be [REDACTED] respectively. Note that in primary analysis, the

response rate is estimated using NRI-C which incorporates MI to handle missing data due to Covid-19; then the number of responders (n) is calculated based on the total number of subjects and estimated response rate, without rounding to an integer, to calculate the posterior probability.

Then the posterior probability is given by

$$\text{Posterior Probability} = \frac{\text{Beta}(n + \text{Beta prior}, m + \text{Gamma prior})}{\text{Beta}(n + \text{Beta prior}, m + \text{Gamma prior}) + \text{Beta}(n + \text{Beta prior}, m + \text{Gamma prior})}$$

where $B(p, q)$ is the Beta function with parameters p and q, δ is corresponding to the pre-specified treatment difference under the proposed alternative hypothesis.

The posterior mean difference will be determined as $\bar{x}_{\text{ravagalimab}} - \bar{x}_{\text{placebo}}$.

In addition, CI_U credible interval for $\theta_{\text{ravagalimab}} - \theta_{\text{placebo}}$ will be calculated from

$$\text{CI}_U = \bar{x}_{\text{ravagalimab}} - \bar{x}_{\text{placebo}} + \text{Beta prior} - \text{Gamma prior}$$

and

$$\text{CI}_L = \bar{x}_{\text{ravagalimab}} - \bar{x}_{\text{placebo}} - \text{Beta prior} + \text{Gamma prior}$$

where CI_U and CI_L are CI_U credible interval upper limit and lower limit.

Similar comparison will be performed using Beta prior prior for placebo group. Note that if observed response rates in ravagalimab group and historical placebo group are both zero, no comparison will be performed using Bayesian approach.

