### Sample Size Estimation and Decision Probability

The planned sample size is up to approximately 40 subjects.

Meta-analysis for historical placebo data from tofacitinib (OCTAVE1/2), upadacitinib (Phase 2b; data on file) and ustekinumab (UNIFI) studies gives [REDACTED] endoscopic improvement rate at Week 8. The matched prior distribution for placebo is [REDACTED]. The prior for ravagalimab treatment group will be set to Jeffreys prior Beta (0.5, 0.5) as non-informative. The probability that the posterior probability of rate difference  $> 0$  is larger than 90% is more than 90% if the endoscopic improvement rate difference is 25% between ravagalimab and historical placebo, given a sample size of 40 subjects for ravagalimab. If ravagalimab has the same endoscopic improvement rate of [REDACTED] as historical placebo, that probability is approximately 3.1%.

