8.2 Handling of Missing Data

Missing data imputation will be done only for efficacy variables (categorical and continuous variables). For the analysis other than efficacy, no imputation will be done for missing values.

Censoring

For the time-to-event endpoint, i.e., time to clinical response per Partial Adapted Mayo score, missing data will be considered as censored at the last available time for the information.

Non-Responder Imputation incorporating Multiple Imputation to handle missing data due to COVID-19 (NRI-C)

The NRI-C will categorize any subject who does not have an evaluation during a pre-specified visit window (either due to missing assessment or due to early withdrawal from the study) as a non-responder for the visit. In addition, at or after the UC-related corticosteroids intercurrent event (see Section 8.1), subjects will be counted as non-responders. The only exception is that missing data due to COVID-19 infection or logistical restrictions related to the COVID-19 pandemic will be handled by Multiple Imputation (MI). At each visit, subjects will be characterized as responders or non-responders based on MI imputed values if missing due to COVID-19; otherwise, subjects will be considered as non-responders for missing due to other reasons in the NRI-C approach.

Mixed-Effect Model Repeated Measurements (MMRM)

MMRM analysis will be conducted using mixed-effect model including observed measurements at all visits. For the MMRM analysis, data collected at or after UC-Related corticosteroids intercurrent event will be excluded. The mixed model includes the categorical fixed effects of visit, baseline corticosteroid use (yes vs no), baseline Mayo endoscopic sub-score (2 vs 3), the continuous fixed covariate of baseline measurement and treatment and treatment-by-visit interaction, if applicable. An unstructured variance covariance matrix will be used. If there is a convergence issue, a compound symmetry structure and a variance components structure will be considered in sequence. The parameter estimations are based on the assumption of data being missing at random and using the method of restricted maximum likelihood (REML).

As Observed (AO)

The AO analysis will not impute values for missing evaluations, and thus a subject who does not have an evaluation on a scheduled visit will be excluded from the AO analysis for that visit. All observed data will be used in the analysis.

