8.3.3 Primary Analysis of the Primary Efficacy Endpoint

Analysis of the primary efficacy endpoint will be conducted on the FAS. Comparison of the primary efficacy endpoint will be performed between the ravagalimab group and the historical placebo group using Bayesian approach with placebo distribution [REDACTED] from historical data meta-analysis and prior for ravagalimab Beta (0.5, 0.5), the Jeffrey's prior for binomial distribution. The posterior probability of rate difference > 0 given data, i.e., $P(\theta_{ABBV-323} - \theta_{Placebo} > 0 | data)$ will be calculated. In addition, the mean difference and 95% credible interval for the mean difference will be provided.

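### The primary posterior treats COVID-imputed Week 8 outcomes as observed, so its credible interval is somewhat too narrow whenever any outcome is imputed

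*SAP*

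**What the plan says.** SAP 8.2 defines NRI-C. A missing evaluation counts as non-response, and so does any outcome at or after a UC-related corticosteroid event. The one exception is data missing because of COVID-19 infection or pandemic logistics, which "will be handled by Multiple Imputation (MI"). SAP 8.3.2 applies NRI-C to the primary endpoint.

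SAP 8.3.3 compares ravagalimab with historical placebo through the posterior probability that the rate difference exceeds zero, and adds that the mean difference and "95% credible interval for the mean difference will be provided". Appendix D3 links the two parts: the NRI-C response rate times the total number of subjects gives the number of responders n, which is used "without rounding to an integer, to calculate the posterior probability". No step in either document combines posteriors over imputations, adds between-imputation variance or reduces N. SAP 8.4 carries the same Bayesian method with NRI-C to the binary secondary endpoints, where applicable.

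SAP 8.3.4 repeats the Bayesian analysis on as-observed data as a sensitivity analysis. Its supplementary Bayesian analysis is described only by a different placebo prior.

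**The concern.** Every completed data set has an integer responder count. A fractional n therefore points to a rate averaged over imputations and used once. Each imputed subject then adds as much information as a subject with a centrally read endoscopy. Multiple imputation is used so that uncertainty about the unseen outcomes reaches the result, and a single update at the average removes it.

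The quantities affected are those that SAP 8.3.3 reports for the primary endpoint. The 0.90 level also defines the operating characteristics in Protocol 7.3 and SAP Appendix D, so a posterior probability that is a little high would be read against that mark.

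**Working it through.** **Inputs.** Protocol 7.3: "The planned sample size is up to approximately 40 subjects", and "The prior for ravagalimab treatment group will be set to Jeffreys prior Beta (0.5, 0.5) as non-informative". The placebo prior is redacted. Appendix D2 says that "20 historical subjects or less could be borrowed while controlling false positive rates" below 10%, so I take effective size 20. Appendix D1 describes the original meta-analysis as "in a total of 325 placebo subjects" and shows 4/65, 4/65 and 11/161. That is 19/291, which leaves 325 − 291 = 34 subjects with redacted responders. If 0 to 4 of them responded, the pooled rate is 19/325 = 5.8% to 23/325 = 7.1%.

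**The plan's own figure.** With placebo Beta(1.2, 18.8) (mean 6%, size 20) and ravagalimab Beta(r + 0.5, 40 − r + 0.5), the smallest r with posterior probability above 0.90 is 6. The chance of 6 or more responders in 40 is 3.09% at a true rate of 6% (stated: about 3.1%) and 99.4% at 31% (stated: more than 90%). This prior is consistent with the protocol but not proven; at a 6% mean, sizes 30 and 40 give the same cut-off. The SAP has since updated the primary prior, so I show means of 5%, 6% and 7%.

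**The two posteriors.** Let x respond among N − k observed, with k outcomes imputed from the observed-data posterior. Put m = (x + 0.5)/(N − k + 1).

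- D3 as written: n = x + k·m, posterior Beta(n + 0.5, N − n + 0.5), with mean m and variance m(1 − m)/(N + 2).
- Completed-data posteriors averaged over imputations: Beta(x + 0.5, N − k − x + 0.5), with mean m and variance m(1 − m)/(N − k + 2).

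The centre is the same; only the spread differs.

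**One case in full: N = 40, k = 6, x = 5, 6% prior.** m = 5.5/35 = 0.157 and n = 5.94. The ravagalimab variance is 0.157 × 0.843/42 = 0.00315 as written and 0.157 × 0.843/36 = 0.00368 when averaged. The placebo variance is 0.06 × 0.94/21 = 0.00269. The SD of the difference is 0.0764 against 0.0798, a ratio of 1.044. Numerically, the 95% interval is −0.065 to 0.243 as written and −0.068 to 0.253 when averaged, so the former is 4.2% too narrow. The posterior probability is 0.904 against 0.898. The completed data sets themselves range from 0.859 (no imputed responder, weight 0.385) through 0.906 (one, weight 0.368) to 0.939 (two, weight 0.179) and above.

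**Range.** Probabilities are as written / averaged, for x = 5. The last column is the shortfall in interval width over x = 3, 5 and 10 and all three priors.

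| k | prior 5% | prior 6% | prior 7% | interval too narrow by |
|---|---|---|---|---|
| 1 | 0.900 / 0.899 | 0.866 / 0.865 | 0.829 / 0.828 | 0.5–0.8% |
| 2 | 0.906 / 0.904 | 0.874 / 0.872 | 0.838 / 0.835 | 1.1–1.6% |
| 4 | 0.918 / 0.915 | 0.889 / 0.885 | 0.856 / 0.851 | 2.2–3.3% |
| 6 | 0.930 / 0.925 | 0.904 / 0.898 | 0.874 / 0.867 | 3.5–5.1% |
| 8 | 0.941 / 0.934 | 0.919 / 0.910 | 0.892 / 0.883 | 4.9–7.0% |

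For x = 5 the overstatement is 0.001 to 0.010. It reaches 0.013 for x = 3 and stays below 0.002 for x = 10.

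**The case against.** The strongest reply is that the plan already contains the right answer. If every missing outcome is COVID-related and no corticosteroid event applies, the averaged posterior above is exactly the as-observed posterior of SAP 8.3.4, and a reader would see both values. That holds only in this simple case. Suppose 32 outcomes are observed with 5 responders, 2 are missing for other reasons and set to non-response, and 6 are imputed from the observed rate (6% prior). D3 gives 0.906, the averaged posterior 0.900 and the as-observed analysis 0.910. A sensitivity analysis also does not correct the primary one.

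The second reply is that little depends on it. A reader might infer that the shortcut could turn a failed study into a success at 0.90. The documents do not support that. Protocol Appendix E records that the success criterion was removed, SAP 8.3.3 sets no cut-off, and SAP 11.0 names no threshold for the interim. A crossing also depends on the prior and the counts: 5/34 with six imputed straddles 0.90 at a 6% prior mean, but not at 5% or 7%.

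Third, COVID-related loss may be small. The Operations Manual (2.1 and 3.15) allows endoscopy at a local center and longer windows. Neither document gives an expected count, so k = 1 to 8 is my assumption.

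Finally, part of the reading is inferred. Averaging over imputations follows from the fractional count and is not stated. The fractional-count sentence names only the posterior probability; the interval follows because it describes the same posterior, and its formula is illegible. The SAP states neither the imputation model nor the number of imputations. Informative covariates would reduce the variance lost.

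**Conclusion.** The point stands as a small, conditional error in the primary analysis as written. It is nil without COVID-missing Week 8 outcomes and does not touch outcomes fixed as non-response. With N = 40, a placebo prior of mean 5% to 7% and size 20, and missing-at-random imputation from the observed rate, the credible interval is about 0.5% to 3% too narrow for 1 to 4 imputed outcomes and about 4% to 7% for 6 to 8. The posterior probability is too high in every case computed, by about 0.001 to 0.010 with five observed responders. This affects the precision that is reported; the documents do not show that it would change a decision. It is worth correcting because the rule discards the variance that multiple imputation is meant to carry, and nothing else in the plan restores it.

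**What to change.** Replace the fractional-count sentence in Appendix D3. In each imputed data set, update Beta(0.5, 0.5) with that data set's integer responder count. Pool the posterior draws with equal weight across imputations, and take the posterior probability, mean difference and 95% credible interval from the pooled draws. Apply the same rule to the binary secondary endpoints analysed with NRI-C under SAP 8.4. State the imputation model and the number of imputations in SAP 8.2. The cost is a few lines of code, a short SAP edit and a slightly wider interval; no new data are needed and the estimand is unchanged.
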